Evaluating the Efficacy of Lateral Heel Wedges for Osteoarthritis of the Knee

NCT: 02254473 March 1, 2014

Evaluating the Efficacy of Lateral Heel Wedges for Osteoarthritis of the Knee

Principal Investigator: [name]

Significance

Given the prevalence of osteoarthritis of the knee and the general aging trends of the population it is important to develop effective non-operative interventions to reduce pain and improve function in the adult population with osteoarthritis (OA) of the knee. A large body of experimental evidence documents the potential for cartilage regeneration in the osteoarthritic joint under conditions of mechanical unloading of the involved joint. An easily applied, off-the-shelf shoe insert material that, when configured properly, will unload the medial compartment of the knee has been developed. The purpose of this investigation is to document the acceptability and effectiveness (with patient reported measures) of this insert compared to a control insert which does not unload the medial compartment of the knee in a group of patients with significant OA of the medial compartment of the knee in order to develop pilot data to document the effect size, acceptability of the inserts, compliance, feasibility, and power for a future clinical trial. Following communication with NIAMS officials we plan to submit an R34 proposal for this purpose. Multiple clinical trials measuring the impact of shoe inserts on knee OA symptoms report minimal benefit. These trials are conducted in a manner which used: 1. self-reported OA, 2. subjects not presenting for treatment and 3. Not in a stratified population of patients with moderate to severe medial compartment OA. Our study selects for patients with this moderate to severe medial compartment OA who pass the screening test of sufficient MCL laxity to allow correction of the weight bearing axis. Further the material used in these inserts is of a different stiffness which is molded to that of the human heel pad. This clinical trial will likely never be industry funded because of the inexpensive nature of the intervention.

Objectives and Hypothesis

Regularly wearing a 5 degree sloped insole over the course of one year will result in a wider joint space by x-ray in 60% of the subjects, a significant decrease in knee pain, decreased use of over the counter analgesics, and a clinically important 2 point improvement in the Womac pain and stiffness scale.

Methods

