We will recruit 80 adults with Kellgren-Lawrence changes between grade 2-4 medial compartment osteoarthritis of the knee from the TRIA Orthopaedic Center in Minneapolis, MN. The subjects will be randomized to a 5 degrees lateral wedge shoe insert or a flat shoe insert of similar properties through a random table generator application which will be coordinated through the TRIA Orthopaedic Center.

Inclusion Criteria:

- Adult patients 30 years or older with symptomatic medial compartment knee osteoarthritis and Grade 2-4 Kellgren-Lawrence radiographic changes presenting for treatment of knee pain.
- Range of motion knee-flexion beyond 100 degrees and not lacking more than 15 degrees of extension.
- Subtalar and forefoot motion permitting foot/ankle eversion with weight bearing.
- Sufficient shoe toe box height to allow space for the insole and therefore comfort and compliance.
- Passive laxity of medial capsule and collateral ligament by knee extension test.

Exclusion Criteria:

- All other forms of knee arthritis other than osteoarthritis.
- Bilateral symptomatic osteoarthritis of the knee.
- Knee Instability- medial pseudo-opening of greater than grade 1 or detectable anterior-posterior instability.
- Less than Grade 2 Kellgren-Lawrence radiographic changes in the medial compartment of the knee.
- Kellgren-Lawrence radiographic changes that are greater than or equal to the medial compartment in either the patellofemoral or lateral compartment.
- Inadequate knee range of motion as demonstrated on exam.
- Balance problems requiring the use of a walker or wheel chair (ambulation with aid).
- Diabetes with peripheral neuropathy.
- History of knee arthroscopy on the index knee within the past three months of study enrollment.
- History of reconstructive (ligamentous etc.) knee surgery within one year of enrollment.
- Intra-articular steroid injection or visco supplementation on the index knee within 1 month of study enrollment.
- Stiff subtalar or forefoot joints as demonstrated on clinical exam.
- Inadequate shoe toe box depth to accommodate the shoe insoles.
- Charcot joint.
- Fixed contracture of the medial capsule and/or collateral ligament as demonstrated on clinical exam.

Rationale for Inclusion:

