This group would otherwise be candidates for surgical intervention. Those with end stage osteoarthritic lesion would have biological potential for restoration of the cartilage. They would have range of motion that provided near normal gait and flexion enough to rise out of a chair. The insole fitting would accommodate the candidate's foot anatomy, any pathology and the geometry of their shoe.

Rationale for exclusion:

This criterion removes those conditions that would have potential to add conflicting data to the study and/or produce discomfort for the subject.

Statistical analysis plan:

All analyses will be done using S.A.S. (version 9.2) and two-sided p-values of less than 0.05 will be considered statistically significant. Appropriate descriptive summary statistics (including means and s.d.) and graphs (including histograms, kernel smoothed density plots, error bar plots) will be utilized to summarize Womac pain, stiffness and function in each treatment group at baseline, 6 month visit and 12 month visit. We will consider a linear regression using the generalized estimating equation (gee) approach to estimate the Womac pain, stiffness and function differences between wedge insert and flat insert groups with intention-to-treat principle. We selected gee as the primary approach as it accounts for the potential correlations among repeated measures within subjects. In addition, it has been shown the gee is more efficient compared to the two sample t-test, the paired t-test, the analysis of covariance (including treatment and baseline response as covariates), and is asymptotically equivalent to the analysis of covariance ii (including treatment, baseline response and an interaction between treatment and baseline response as covariates) 40. Missing data will be handled with multiple imputation using S.A.S. proc mi and mianalyze. Secondary outcomes will include clinical and functional outcomes with standardized knee radiographs, a validated University of Minnesota pain and acceptability scale, a medication log in terms of weekly hours of insert usage will be analyzed similarly and the Tegner Activity Scale to document any change in activity level in addition to the function addressed in the other outcomes instruments

Test Intervention:

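### The efficiency claimed for the primary GEE depends on how baseline WOMAC enters the model, and the plan gives baseline no role

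*Combined protocol and SAP*

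**What the plan says.** The statistical analysis plan section states the primary analysis in one sentence: "We will consider a linear regression using the generalized estimating equation (gee) approach to estimate the Womac pain, stiffness and function differences" between the two insert groups, by intention to treat. It gives two reasons for GEE. The first is that "it accounts for the potential correlations among repeated measures within subjects". The second is efficiency: "it has been shown the gee is more efficient compared to the two sample t-test, the paired t-test, the analysis of covariance". The same sentence then claims asymptotic equivalence to the ANCOVA that includes a treatment-by-baseline interaction (ANCOVA II), citing reference 40. By its title, that reference concerns pretest-posttest trials.

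The model sentence contains no baseline term, visit term, arm-by-visit term, working correlation or target visit. In that section, baseline WOMAC appears only among the time points to be summarised descriptively (baseline, 6 and 12 months) and in the definitions of the ANCOVA comparators. The later Statistical Analysis section adds standard approaches and regression on medication use and insert-wearing time, again without baseline WOMAC. Missing data go to multiple imputation, with no imputation model given. Subject Instructions and Table 2 show WOMAC collected at enrollment and at five later visits.

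**The concern.** GEE is a way of fitting a mean model to correlated data. If each arm has a free mean at each visit and the data are complete, it returns the raw differences in arm means whatever working correlation is used. Precision improves over the unadjusted comparison at a given visit only when the model uses baseline information, as a covariate or through a common pre-randomisation mean. The efficiency argument therefore supports one particular model, and the plan does not write that model down.

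The unwritten choice affects both the precision and the meaning of the estimate. The Significance section says the study is to document the effect size and power for a later trial, and the plan to follow it with a planning grant says its data will be used to calculate that trial's subject numbers. An imprecise or diluted estimate would carry straight into that calculation. Leaving the model open also lets it be chosen among different estimands after the data are seen.

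**Working it through.** **Inputs from the documents.** Total sample 80 (Methods: "We will recruit 80 adults with Kellgren-Lawrence changes"). Two-sided 0.05 ("two-sided p-values of less than 0.05 will be considered statistically significant"). WOMAC at baseline and five follow-up visits. The plan has no power, SD or correlation figure to reproduce. The hypothesis refers to "a clinically important 2 point improvement in the Womac pain and stiffness scale" but gives no scale version or SD, so effects are in SD units here.

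**Assumptions.** 1:1 allocation (40 per arm; the ratio is not stated), complete data, equal SD at every visit, a common between-visit correlation r of 0.3, 0.5 or 0.7, and a true effect of 0.5 SD that is constant over follow-up. Power is from the noncentral t with 78 degrees of freedom.

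**Base case.** The SE of a difference at one visit is √(2/40) = 0.224 SD. Each reading multiplies the variance by the factor shown.

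| Reading of the model | Expected estimate | Variance factor | SE at r = 0.3 / 0.5 / 0.7 | Power |
|---|---|---|---|---|
| A. Follow-up only, arm-by-visit terms, 12-month contrast | 0.50 | 1 | 0.224 at each r | 60% at each r |
| B. Baseline as a response, full arm-by-visit terms (change score) | 0.50 | 2(1−r) | 0.265 / 0.224 / 0.173 | 46 / 60 / 81% |
| C. One arm effect pooled over 6 and 12 months, no baseline | 0.50 | (1+r)/2 | 0.180 / 0.194 / 0.206 | 78 / 72 / 67% |
| D. One arm effect pooled over five follow-up visits, no baseline | 0.50 | (1+4r)/5 | 0.148 / 0.173 / 0.195 | 91 / 81 / 72% |
| E. Baseline, 6 and 12 months as responses, one arm coefficient | 0.50 × 2/3 = 0.33 | (1+2r)/3 | 0.163 / 0.183 / 0.200 | 52 / 44 / 38% |
| F. All six visits as responses, one arm coefficient | 0.50 × 5/6 = 0.42 | (1+5r)/6 | 0.144 / 0.171 / 0.194 | 81 / 67 / 57% |
| G. Baseline as covariate, or as response with a common mean; 12-month contrast | 0.50 | 1−r² | 0.213 / 0.194 / 0.160 | 64 / 72 / 87% |

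**G against A.** The variance ratio 1−r² is 0.91, 0.75 and 0.51. An unadjusted analysis would need 80/(1−r²) = 88, 107 and 157 patients to match the adjusted analysis of 80.

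**G against B.** The ratio is (1−r²)/(2(1−r)) = (1+r)/2 = 0.65, 0.75 and 0.85. B beats A only when r exceeds 0.5.

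**C with baseline added.** The factor becomes (1+r)/2 − r². At r = 0.5 that is 0.50 instead of 0.75, and power rises from 72% to 88%. C gains over A by averaging visits, and it equals a t-test on each patient's follow-up mean. It still leaves the baseline information unused.

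**Simulation check.** 600 trials, 40 per arm, three visits, r = 0.5, effect 0.5 SD, GEE with exchangeable working correlation:

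- Reading A matched the t-test difference to machine precision (empirical SE 0.2255 for both).
- Reading C had SE 0.190.
- Reading E averaged 0.339.
- Reading G, as a common-baseline-mean GEE, had SE 0.1925, against 0.1919 for ordinary ANCOVA and 0.1921 for ANCOVA II.

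**The case against.** The strongest reply is that the authors meant a GEE that uses baseline. Equivalence to ANCOVA II can hold only for such a model, and the pretest-posttest title of reference 40 points the same way. On that reading the analysis reaches ANCOVA precision and loses nothing. This stands as evidence of intent. It does not supply a specification: an analyst could not recover from the text whether baseline is a covariate, a constrained response or an ordinary response, and these give different answers.

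A reader might infer something stronger, that the model as written must either be no more precise than a t-test or dilute the effect. The documents do not support that. No complete model is written, so several can be fitted. Readings C and D beat a single-visit t-test, B is an undiluted change score, and G is fully efficient.

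The dilution figure also depends on the reading. The one-third loss takes the three time points named for descriptive summaries; the one-sixth loss takes all six. Both assume a constant effect, although Study Procedures has the wedge group in 2.5-degree insoles until week 6. Under the six-visit reading the estimate is too small, yet power at r = 0.5 is 67% against 60% for the t-test. There the harm is to the effect estimate, not to the test.

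Finally, it would be tempting to call superiority over ANCOVA false outright. The allocation ratio is not stated ("The subjects will be randomized to a 5 degrees lateral wedge shoe insert or a flat shoe insert of similar properties"), and the plan's claim rests on a source not examined here. What can be said is that under equal allocation there is no material gain over ordinary ANCOVA.

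**Conclusion.** The concern holds as a defect of specification. The plan selects its primary method on an efficiency argument that is true only for a baseline-using model, and it does not state such a model. Depending on the reading, the analysis could match a t-test exactly, understate a constant effect by up to a third, or reach ANCOVA precision. At 12 months, adjustment is worth a variance reduction of 9% to 49% for correlations of 0.3 to 0.7.

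These sizes rest on assumed 1:1 allocation, complete data, equal SDs and the assumed correlations; the documents give none of them. That the gain over the t-test requires baseline to be used does not depend on those values. Because the study is a pilot, the main consequence is for the effect size handed to the definitive trial. The change should be made, but its absence does not invalidate the study.

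**What to change.** Replace the model sentence with a full specification:

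- Regress each follow-up WOMAC subscale on arm, visit (categorical), arm-by-visit, that subscale's baseline value and baseline-by-visit. Alternatively, keep baseline as a response with its mean constrained equal across arms.
- Name the visits that enter the model and the working correlation.
- Name the target contrast, for example the 12-month difference between arms.
- Include baseline WOMAC in the imputation model.
- Limit the efficiency statement to the comparison with unadjusted and change-score analyses, and drop the claim of superiority over ANCOVA.

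No Kellgren-Lawrence covariate is needed for this fix. The cost is a few sentences of SAP text. Baseline WOMAC is already scheduled for every patient, so no data collection changes.

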The Insoles: A commercially available proprietary insole in the form of a slab 10.5 cm wide and 35.5 cm. long will be used. They are available in two geometries and materials. The control insole is blue in color with a thin felt cover to be next to the subject's skin. It is 3 mm level depth side to side and front to back. The material is a proprietary material known commercially as Poron® with a durometer of 25; the average durometer of the human foot is 25-35 depending upon the thickness of the plantar soft tissue and the presence of bone beneath.

The experimental insole is a slab is green in color and made of polyvinyl acetate with a felt layer opposite the patients skin. It has a 5 degree wedge and is 3 mm high on thin side and 10 mm high on the other side. This insole will be fitted with the pattern cut so the outer side of the foot would have the maximum depth of material (the highest side).

Study Procedures:

Patient related: We will recruit 80 subjects presenting for treatment of knee who have primary OA of the knee primarily involving the medial compartment and meet the inclusion criteria. The will be randomized via a random table generated computer program to the wedge inserts or the flat inserts. They will be screened for adequate knee laxity and subtalar motion before enrollment at each site.

Subjects, experimental and control, will complete the Womac based on their current function, have bilateral standing knee radiographs obtained in a standardized fashion and be fit with the inserts and instructed to return in 6 weeks to have new inserts fashioned. The patient contact will be performed by the clinical coordinator. At the 6-week visit, the patients randomized to the wedge insole will have the 5 degrees insoles fit after their 6-week adjustment period with the 2.5 degrees insoles while those in the control group will be fit with new inserts.

At 3, 6, 9 and 12 months, all patients will return for new inserts and to complete secondary radiographs (6 months only) and to turn in their shoe insert acceptability, use logs and medication logs. Patients will be supplied with as many inserts as they need to assure that the shoes they wear on a daily basis are included.

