Our podiatry consultant will be involved with the training of the research coordinator for patient screening for adequate knee medial laxity and subtalar motion as well as proper fitting of the inserts. He will be the primary contact for questions during the trial related to insert fit. We will hold a one day meeting at TRIA Orthopaedic Center in Minneapolis for the site investigator to review study procedures emphasizing patient screening and consent, procedures for standardizing radiographs, and the technique for application of the shoe inserts and procedures for managing drop out of patients.

Procedures for standardization of subject screening and recruitment, application of test and control inserts; radiographic measure will be done at a one day meeting for the staff at TRIA Orthopaedic Center. The details of the administration of the U of MN pain scale, shoe insert use log, insert acceptability scale, medication log, Tegner and Womac will be reviewed.

With approval from NIAMS officials, we intend to follow this proposal with an R34 submission in order to plan the definitive clinical trial using the data from this proposal to develop a detailed Manual of Operations, calculate the subject numbers we will need to recruit, the estimated number of subjects we might lose to the one year follow-up requirement, the number of additional clinical sites needed to recruit the cohort within a 6 month period, and develop statistical approaches to manage confounding variables such as patient BMI, activity levels, and medical comorbidity.

Table 2:

	Initial visit (Randomization)	6 week	3 month visit	6 month visit	9 month visit	12 month visit
WOMAC, Tegner, and Pain scale	S	S	S	S	S	S
Standing AP bilateral	Р	Х	X	S	Х	Х
Lateral Affected knee	Р	Х	X	S	Х	Х
Medication log	Х	S	S	S	S	S
Shoe insert log	Х	S	S	S	S	S
Clinic visit	Р	S	S	Р	S	Р
MRI						S

P = patient expense; S = study expense; X = not done

Benefits of this intervention and study design:

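### The plan appears to impute missing insert-wear hours with no rule separating stopped use from a missing log, so compliance may be overstated

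*Combined protocol and SAP*

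**What the plan says.** The Statistical analysis plan section names the main model for WOMAC: "We will consider a linear regression using the generalized estimating equation (gee) approach to estimate the Womac pain, stiffness and function differences", by intention to treat. It then gives one general rule for missing values: "Missing data will be handled with multiple imputation using S.A.S. proc mi and mianalyze". That rule is not limited to WOMAC. The next sentence lists the secondary outcomes and says that "a medication log in terms of weekly hours of insert usage will be analyzed similarly".

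Wear data come from the patients. Under Study Procedures, "At 3, 6, 9 and 12 months, all patients will return for new inserts", and the same sentence has them attend "to turn in their shoe insert acceptability, use logs and medication logs". Table 2 has a row headed "Shoe insert log", separate from the medication log, with collection at 6 weeks and at 3, 6, 9 and 12 months.

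The Significance section states what the pilot is for: to "document the effect size, acceptability of the inserts, compliance, feasibility, and power for a future clinical trial". The later Statistical Analysis section also treats time of insert use as a confounding variable to be handled by regression.

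Nowhere do the documents say how hours are counted after a patient stops wearing the inserts, specify the imputation model, or plan a sensitivity analysis for missing logs. Drop-out procedures are listed as a training topic but are not described.

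**The concern.** When a WOMAC score is missing, the value behind it is unknown. Wear hours differ: once a patient is known to have stopped, the value is known, and it is 0. Standard imputation predicts a missing value from patients who still return logs, most of whom are still wearing the inserts. A stopper with no log is therefore given positive hours, and these are the patients who define non-compliance.

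Stopping and a missing log may well go together. Logs are handed in at visits where new inserts are fitted, and Table 2 marks the 6- and 12-month clinic visits as patient expense. Someone who has given up the inserts has less reason to attend. This is a plausible mechanism, not one that the documents state.

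Three things are at stake. Compliance is a named product of the pilot and feeds the planning of the definitive trial. The same hours enter the regression on time of use, so false hours would carry over into that analysis. And the error is larger in whichever arm has more silent stoppers, so a real difference in wear between wedge and flat inserts could be hidden.

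**Working it through.** The plan gives no figure for wear hours, stopping or missing logs, so there is nothing to reproduce. What follows is an illustration, and all its inputs are assumptions.

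**Inputs (assumed)**
- Patients still wearing inserts average 40 h/week at 12 months.
- A share f has stopped: 10%, 20% or 30%. Their true value is 0.
- A share u of the stoppers returns no log. The rest return a log showing 0 hours.

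**Step 1: true mean.** 40 × (1 − f) = 36, 32 and 28 h/week.

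**Step 2: impute at the mean of the returned logs.** That mean is 40(1 − f) / (1 − fu), so the relative overstatement is fu / (1 − fu).
- u = 0: no overstatement.
- u = 0.5: 0.05/0.95, 0.10/0.90 and 0.15/0.85, or about 5%, 11% and 18%.
- u = 1: 0.10/0.90, 0.20/0.80 and 0.30/0.70, or about 11%, 25% and 43%.

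**Step 3: let the imputation use earlier hours, with u = 1.** Assume SD 12, correlation 0.6 between earlier and 12-month hours, and stoppers 0.5 SD lower early on. Stoppers are then imputed at 40 − 0.6 × 0.5 × 12 = 36.4 h/week.
- f = 10%: 0.9 × 40 + 0.1 × 36.4 = 39.6, and 39.6/36 gives 10% too high.
- f = 20%: 0.8 × 40 + 0.2 × 36.4 = 39.3, and 39.3/32 gives 23% too high.
- f = 30%: 0.7 × 40 + 0.3 × 36.4 = 38.9, and 38.9/28 gives 39% too high.

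| Stopped | True mean (h/week) | All stoppers return a zero log | Half do | None do (step 3) |
|---|---|---|---|---|
| 10% | 36 | 0 | 5% | 10% |
| 20% | 32 | 0 | 11% | 23% |
| 30% | 28 | 0 | 18% | 39% |

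**Step 4: simulation of the imputation itself, with u = 1.** One arm of 40 patients (80 in total, equal allocation assumed), five visits, wearers' mean 40 h/week, between-patient SD 10, within-patient SD 6, regression imputation for dropout-type missingness, 10 imputations, 400 replicates. Overstatement at 12 months for 10%, 20% and 30% stopping:
- stoppers' earlier hours like everyone else's: 11%, 25%, 45%;
- stoppers 10 h/week lower beforehand: 9%, 20%, 33%;
- stoppers 20 h/week lower beforehand: 7%, 14%, 25%.

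Early low use reduces the bias but does not remove it. The mean of the returned logs alone was about 40 h/week in every one of these scenarios, so it was biased about as much as imputation or more.

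**Step 5: between arms.** Suppose 10% stop in one arm and 30% in the other, with u = 1 and the step 3 model. The true difference is 36 − 28 = 8 h/week. The imputed difference is 39.6 − 38.9 = 0.7 h/week.

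**The case against.** The strongest reply is that the plan may not impute wear hours at all. The sentence on weekly hours is garbled: it describes insert use as a medication log, while Table 2 keeps two separate logs, and the similarity it claims could be to the GEE model only. That is a fair caution, and application to wear hours remains an inference. It is still the plain reading, because the imputation rule just before it is unrestricted. Nor would the narrower reading remove the problem, since returned logs alone are biased as much or more.

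Second, the visits are not only for collecting inserts. Table 2 schedules WOMAC, Tegner, the pain scale and the medication log at every follow-up, so a patient who has stopped has reason to attend and can return a log showing zero. This stands. If all stoppers do so, the bias is nil.

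Third, a missing log is not proof of non-use. A patient may miss a visit and keep wearing the inserts, and scoring every missing log as 0 would then understate wear. This also stands, and it limits the remedy.

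Fourth, the documents do not say that compliance will be reported as an imputed mean of hours. True, but weekly hours are the only wear measure given an analysis.

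A reader might go further and infer that the compliance result is bound to be overstated, or that imputation itself creates the error. The first needs a stopping and non-return rate that the documents do not give. The second fails because returned logs alone do no better. Nor do the documents support scoring a stop for discomfort as unacceptable on the acceptability scale, because its scoring is not given.

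**Conclusion.** The point holds in conditional form. On its plain reading the plan imputes missing wear hours and has no rule that separates stopped use from a log missing while use continues. Whenever a patient stops and returns no log, following the plan gives a wrong value to a measure that the pilot exists to produce.

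The size is unknown. With wearers at 40 h/week and 10%, 20% or 30% stopping, it runs from zero, if all stoppers return zero-hour logs, to about 10%, 23% and 39% if none do. The upper figures depend on every stopper being silent and on the assumed correlation and early-use gap; other assumptions in the working move them both up and down. Given silent stoppers, the direction was upward in every case examined. The root of the problem is the missing rule for hours after stopping, not the choice of multiple imputation. It should be put right, but it does not undermine the WOMAC comparison as such.

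**What to change.** Add to the SAP, and to the existing shoe insert log:

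1. A field for the date insert use stopped, completed at any study contact.
2. Hours set to 0 from a documented stop date onward.
3. Multiple imputation of wear hours only for logs missing when the patient was not known to have stopped.
4. By visit and arm, the number of logs returned and the proportion still wearing inserts, shown beside mean hours.
5. A sensitivity analysis with all missing logs set to 0 hours. This gives a low bound that covers patients who stop without telling anyone, whom the main analysis would still impute.
6. The same derived hours used in the regression on time of use.

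The sentence on weekly hours should also be rewritten to name the shoe insert log and to say whether imputation applies to it.

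The cost is one extra field, a little more analysis and, if patients do stop, a less favourable compliance figure. The field should be in place during follow-up, because stop dates may be hard to recover afterwards.

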At 1 year, a convenience sample of 5 patients in the wedge (treatment) group and 5 patients in the control group who have had prior knee MRI's within 1 year of institution of the treatment shoe inserts will have knee MRI's repeated to check the quality of medial compartment articular cartilage.

Statistical Analysis

The data analysis will be done in a blinded fashion by our statistician. The Womac and Tegner data will be analyzed with standard statistical approaches and confounding variables of medication use and time of use of the shoe inserts will be analyzed with regression techniques. Knee medial compartment width will be measured by two blinded radiologists.

Subject Instructions: Subjects will be informed they are eligible to be part of a study testing various insoles of differing color, material and shape for their impact on arthritic knee pain and function. They will be instructed on insertion and removal of the insoles including printed material of such instructions. After a 6 week run in period utilizing the 2.5 degree lateral wedge test article in order to adjust to the altered weight bearing axis, the subjects will have a 5 degree wedge test article fashioned in the same manner. They will be instructed to return at 3 month intervals for fitting of new insoles and clinical evaluation. X-rays , medication logs, U of MN pain scale¹, Tegner and Womac will be collected at enrollment, 6 weeks, 3 months, 6 months, 9 months and one year.

Tailoring the Insole:

An exam will be performed ensuring the subjects foot and ankle range of motion.

The existing insoles will be removed from both shoes. This method provides maximum toe box height. It also makes a more uniform insole material bilaterally thereby providing consistency. In both groups the insole will be tailored to the subject's anatomy, pathology, and existing shoe geometry. The subjects will be fitted with the tailored insole that extends from the back of the heel to just beyond the metatarsal head, thereby maximizing room in the toe box. Multiple tailoring may be necessary to achieve comfort. The subjects are instructed on the ease of removing and placing the insole so they can move them shoe to shoe, day to day. The insoles will be replaced every 3 months. The Study Coordinator at the local site will have printed instructions to facilitate and perform the fitting of the test and control inserts based on patient randomization.

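### Do the wedge insole's stated angle, edge heights and slab width contradict one another?

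*Combined protocol and SAP*

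**What the plan says.** The Insoles, under Test Intervention, introduces the product used in both arms as a proprietary item "in the form of a slab 10.5 cm wide and 35.5 cm. long will be used". It then describes two versions. Of the control it says "It is 3 mm level depth side to side and front to back". The wedge version is introduced with "The experimental insole is a slab is green in color and made of polyvinyl acetate", and its geometry is given as "It has a 5 degree wedge and is 3 mm high on thin side and 10 mm high on the other side". The next sentence deals with cutting: "This insole will be fitted with the pattern cut so the outer side of the foot would have the maximum depth of material".

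Tailoring the Insole gives only the lengthwise extent of the fitted piece: "The subjects will be fitted with the tailored insole that extends from the back of the heel to just beyond the metatarsal head". No section gives a width for the cut piece, or says whether the slope covers all or part of the slab.

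The 5 degree figure recurs elsewhere. Objectives and Hypothesis is framed around that slope. Methods names the arm by it: "The subjects will be randomized to a 5 degrees lateral wedge shoe insert or a flat shoe insert of similar properties". Subject Instructions says that after the run-in "the subjects will have a 5 degree wedge test article fashioned in the same manner".

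**The concern.** The only width in the documents is 10.5 cm, and it is stated just before the two versions are described. The control's depth is given from side to side, and the wedge's two sides follow in parallel, ahead of the sentence on cutting. A natural reading is that the wedge rises from 3 mm to 10 mm across the full slab. On that reading the heights and width give a slope well short of 5 degrees.

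The angle is the exposure named in the hypothesis and in the label of the randomised arm. If the label were wrong, a result would be reported as the effect of a 5 degree wedge when the wedge worn had another slope. Anyone rebuilding the test article for the planned definitive trial could not satisfy width, heights and angle together.

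**Working it through.** **Inputs**, all from The Insoles: slab width 10.5 cm = 105 mm; thin side 3 mm; thick side 10 mm; so the rise is 10 − 3 = 7 mm; stated angle 5 degrees. No tolerances are given. Where rounding is considered below, it is assumed to be to 1 mm for heights, 0.1 cm for width and 1 degree for the angle.

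**Formula.** Angle = arctan(rise / width).

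**Can the stated 5 degrees be reproduced over the full slab?**
- As stated: arctan(7/105) = 3.81 degrees, which is 1 − 3.81/5 = 24% below 5.
- Rounding most favourable to 5 degrees: arctan(8/104.5) = 4.38 degrees, which still does not round to 5.
- Rounding least favourable: arctan(6/105.5) = 3.26 degrees.
- Rise needed for 5 degrees: 105 × tan(5°) = 9.19 mm. That would mean a thick side of 3 + 9.19 = 12.19 mm, or a thin side of 10 − 9.19 = 0.81 mm.
- Width measured along the slope: arcsin(7/105) = 3.82 degrees, so this makes no difference.

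On the full-slab reading the figures do not agree, and rounding does not rescue them.

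**At what width do they agree?**
- Exactly 5 degrees with a 7 mm rise: 7 / tan(5°) = 80.0 mm.
- Heights rounded: 6 / tan(5°) = 68.6 mm to 8 / tan(5°) = 91.4 mm.
- Angle rounded as well: 6 / tan(5.5°) = 62.3 mm to 8 / tan(4.5°) = 101.6 mm.

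**Slope by width for a 7 mm rise.** Every width except 105 mm is an assumption and does not appear in the documents.

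| Width (mm) | Angle (degrees) | Against 5 |
|---|---|---|
| 70 | 5.7 | 14% above |
| 80 | 5.0 | equal |
| 90 | 4.4 | 11% below |
| 100 | 4.0 | 20% below |
| 105 | 3.8 | 24% below |

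The discrepancy runs in both directions, depending on a width the protocol does not state. Quoting only the 24% shortfall would suggest a weaker wedge than labelled, which the documents do not establish.

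**Does anything in the analysis use the angle?** The Statistical analysis plan compares WOMAC pain, stiffness and function between the wedge and flat groups by GEE, by intention to treat. The later Statistical Analysis section adds medication use and time of insert use as confounders. The angle is not a covariate, a stratum or an input to any calculation.

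**The case for a change.** The best case for asking for a change is that 10.5 cm is the only width a reader is given, and that pattern cutting does not remove the mismatch. A slab that slopes evenly from 3 to 10 mm over 105 mm keeps its 3.8 degree slope however narrowly it is trimmed. Agreement needs a further fact, namely that the heights describe a sloped section or a cut piece about 80 mm wide, and no section says so. The angle also names the exposure, and these data are meant to feed a manual of operations for a larger trial. One sentence would settle the point.

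Most of this stands. The arithmetic is right, rounding alone does not close the gap on the full-slab reading, and the reference width is unstated. What does not stand is the step from an unstated width to a demonstrated error. The slab width comes in a sentence covering both versions. The heights and angle come later, in a paragraph on the wedge alone, and nothing says that the slope spans the slab. Figures that agree under a reading the text allows are not shown to contradict each other. With all three figures rounded, the largest width that agrees (101.6 mm) is only 2.9 mm short of the narrowest slab that rounds to 10.5 cm (104.5 mm). Nor does the definitive trial have to rebuild the insole from this paragraph, because the product is bought in and its manual is still to be written.

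**Conclusion.** This is a gap in a product description, and it needs no change to the plan. If the heights apply to the full 105 mm, the implied slope is 3.8 degrees (3.3 to 4.4 with assumed rounding) against the stated 5. If they apply to about 80 mm, everything agrees. If they apply to less, the slope is steeper than stated. The documents cannot say which case holds, and this review does not say which figure is right. Width, heights and angle have to be reconciled against the product specification or a stock slab, which can be done when the test article is described for reporting or in the later manual.

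Subjects receive an identifiable commercial insole whatever its written dimensions. The wedge-versus-flat comparison is not biased by the omission, every planned analysis is unchanged, and no sample size, power or significance figure moves. The conclusion rests on the trial using that product as supplied, and on the angle serving as a label for the arm and not as an analysed quantity. The documents support both.
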